## 1.0 BACKGROUND AND SIGNIFICANCE

**Fatigue and Ovarian Cancer.** Women diagnosed with ovarian carcinoma (cancer) report multiple quality of life challenges, including persistent fatigue and sleep disturbances. Persistent fatigue is a commonly reported symptom in these women, with as many as 30 to 60% of ovarian cancer survivors continuing to report significant fatigue even several years after the end of treatment. In ovarian cancer, persistent fatigue has been linked to higher levels of chronic pain, lower quality of life, and reduced participation in other self-care activities such as physical activity. Interestingly, risk factors for fatigue post cancer treatment does not appear to be associated with type of cancer, cancer treatment, stage of diagnosis or histopathology of the cancer, but instead with other host factors such as presence of depression or level of physical activity. While the etiology of persistent fatigue in cancer survivors is unknown, recent research in female cancer survivors suggests that cancer related fatigue may involve pathology within the brain, and thus treatments that target the brain may have promise for treating fatigue. Despite the challenges caused by persistent fatigue, there have been very limited attempts to identify self-care-focused interventions, which could improve fatigue, sleep, and quality of life among ovarian cancer survivors. We are proposing to carry out a randomized, controlled trial comparing self-administered acupressure to sham acupressure and no treatment to determine if this is an intervention that survivors can use to address their fatigue.

[figure not shown]

**Figure 1.** A plot of mean weekly fatigue scores for relaxing acupressure (red circles), High Intensity Stimulating Acupressure (closed black circles), and Low Intensity Stimulating (open circles) across study weeks

week depending on group. Fatigue was measured with the Brief Fatigue Inventory on a weekly basis. The change in the Brief Fatigue Inventory was significantly different across groups, with self-administered relaxing acupressure engendering greater reductions in fatigue when compared to acupressure. Deviation acupressure  $2.2 \pm 1.6$ , low  $p=0.027$ ). In either high or low intensity stimulating (See Figures 1 and 2; mean  $\pm$  standard reduction in Brief Fatigue Inventory: relaxing  $4.0 \pm 1.5$ , high intensity stimulating acupressure intensity stimulating acupressure  $2.7 \pm 2.2$ ; linear regression model with change in Brief Fatigue Inventory as the dependent variable, the group difference remained significant after adjusting for age, cancer type, cancer stage, and cancer treatments ( $p=0.013$ ). Across groups, these reductions in fatigue were on the order of 45% to 70%, which are clinically relevant and could represent significant improvements in quality of life for cancer survivors. Acupressure was effective in reducing fatigue in other cancer survivors, including women with ovarian cancer.

[figure not shown]
### Acupressure and Fatigue

Self-administered acupressure is one possible safe, self-management technique for improving persistent fatigue as well as physical and psychosocial functioning in ovarian cancer survivors with chronic cancer-related fatigue. Acupressure, a technique derived from acupuncture, is a component of Traditional Chinese Medicine in which pressure is applied to specific acupoints on the body using a finger or small device to address health issues. Acupressure has shown promise for treating fatigue in cancer patients and survivors, although these have been small studies with numerous methodological flaws including inclusion of multimodal treatment approaches, patients currently receiving or recently completing cancer treatment, and no examination of carry-over effect of acupressure. We performed a pilot intervention of relaxing and stimulating self-acupressure in fatigued adult cancer survivors, of which 14% had been diagnosed with ovarian cancer. In this study, participants were randomized to one of three groups: 1. relaxing acupressure ( $n=14$ ); 2. High intensity stimulating acupressure ( $n=15$ ); or 3. low intensity stimulating acupressure ( $n=14$ ). Participants performed acupressure for 12 weeks between 3 to 14 times per

**Figure 2.** Scatter plot of individual participant BFI change scores (week 12—week 0) indicate greater reductions for relaxing acupressure (red circles), High Intensity Stimulating Acupressure (closed black circles), and Low Intensity Stimulating (open circles).

accuracy with which the acupressure treatment was performed by participants including correct location of acupoints, amount of pressure, duration and frequency of treatments (95% out of 100% on their fidelity ratings), and adherence (performed 73% of all acupressure sessions on average). **These data indicate that acupressure was effective in reducing fatigue in female cancer survivors, and importantly, survivors can be recruited through the Michigan Cancer Registry and a large randomized, controlled study completed. However, no study has examined using a mobile app to teach female cancer survivors to self-administer acupressure — an important innovation to help increase implementation and accessibility for cancer survivors.**

[figure not shown]
**Figure 3.**

Fatigue by Week and Group Assignment. The Brief Fatigue Inventory consists of 9 items, each measuring fatigue on a scale of 0 to 10, and the score is calculated from the mean of completed items. Scores of 4 or higher indicate clinically relevant fatigue. The shaded area represents nonclinical or normal levels of fatigue.

## Self-Administered Acupressure

An advantage of self-acupressure is that once a person learns the technique they are free to control the frequency and dose of the intervention. Since the intervention can be easily learned (generally in less than 15 minutes), we reasoned that an online or mobile application (app) could increase its utilization. In a recent pilot survey of cancer patients with fatigue, use of technology such as a computer program or smartphone app was the most popular response for learning acupressure. Consequently, we developed a mobile app in association with focus groups consisting of cancer survivors (six focus groups consisting each of eight to ten women) and the University of Michigan 3D Media Laboratory. **The acupressure app is called MeTime Acupressure** (Figure 4). One concern with some

Figure 4. Sample MeTime Acupressure Screen

app-based interventions are that the company that initially develops the app may cease to make it available or support it. **Our app was developed at the University of Michigan by the Principal Investigator** and thus there is no chance it will not be available in the future. Importantly, further refinements of the app can be done in an iterative manner.

Focus group participants also asked for a device to accompany the app in order to learn and apply an accurate amount of pressure to each acupoint (the hardest skill to learn for participants and one they expressed as being of high importance).

They also wanted a device that was comfortable to use and could minimize any strain in the hand or fingers from applying the acupressure. To achieve this goal, we partnered with Arbor Medical Innovations (AMI), a Michigan-based technology company to translate their expertise in hand held devices, which provide precise amounts of pressure to create the “AcuWand” device (see Figure 5). The AcuWand is a digital force gauge for the controlled delivery of pressure to discrete acupressure points throughout the body. The AcuWand applies forces from 0-100N, at 100ms intervals, to match the typical

[figure not shown]
delivery of acupressure stimulation and gives feedback through visual and audio cues letting participants know when “too much” or “too little” pressure is being applied. It also incorporates an ergonomic handle so the user can easily grasp the device and apply pressure through a sprung probe with a soft rubber tip. **The AcuWand was designed in collaboration with users and can objectively and comfortably enable ovarian cancer survivors to deliver an adequate amount of pressure to each acupressure point – a critical aspect for performing reliable and efficacious acupressure treatment.**

Figure 5. AcuWand Prototype

## Mechanism of Action of Relaxing Acupressure

It is important to have a “biological rationale” for how stimulating certain areas of the body with a somatic stimulus, such as a finger applying pressure, could actually reduce fatigue any more so than beyond a simple placebo. For instance, a lack of a mechanism could impede the acceptance of, recommendation, and adoption of acupressure by medical professionals. While currently the underlying mechanisms explaining how acupressure improves fatigue and alleviates sleep disruption are unclear, recent research by our group and others provide important clues to systemic and central nervous system processes. A recent review by Zhao suggested that fatigue and sleep effects of acupressure are mediated by a number of neurotransmitters including norepinephrine, melatonin, gamma-aminobutyric acid, and  $\beta$ -endorphin. Animal studies also indicate down-regulation of the hypothalamic–pituitary–adrenal axis, which reduces plasma corticosterone and adrenocorticotropin hormone levels. A heterogeneous and large number of acupoints and methods of stimulating, e.g., needle insertion, electrical acupuncture, moxibustion, acupressure etc., were examined for their mechanistic effects. In general, the type of stimulation appears unimportant, while the acupoint location appears to have some impact on affecting these neuroendocrinological changes.

**Figure 6.** Differential changes in connectivity to the default mode network (DMN) following different acupressure treatments. (A) An independent component analysis of resting state functional MRI data shows increased connectivity between the to the superior colliculus (SC)/periaqueductal gray and the DMN following relaxation acupressure but not stimulating acupressure. Increased connectivity between the DMN and the thalamus (pulvinar) was observed following stimulating but not relaxing acupressure. (B) Scatter plots showing changes in DMN connectivity by acupressure treatment (stimulation: open circles, relaxation: black circles). Connectivity patterns are mutually exclusive: increases in SC-DMN connectivity are accompanied by decreases in pulvinar-DMN connectivity for relaxation acupressure, while the converse

Given the importance of acupoint location it is germane to know that four out of the five acupoints we propose using in the relaxing acupressure formula are commonly used for insomnia in clinical trials: heart 7; spleen 6; liver 3; and Animan, and have demonstrated effects on sleep-related neurotransmitter systems and hypothalamic–pituitary–adrenal axis activity in basic, human and animal studies. Our own small-scale study, which examined the effect of two different types of acupressure--relaxing and stimulating--on fatigue in breast cancer survivors using magnetic resonance imaging, also found that the different types of acupressure (distinguished only by their acupoint locations) work via different mechanisms within the brain. In particular, we found that the relaxing acupressure formula increased the connectivity between the superior colliculus – a brainstem region important in humans and primates that regulates sleep and alertness – and the default mode network – a network of brain regions that is activated when thinking about one’s internal state. In comparison stimulating acupressure decreased this same connection (see Figure 6). Moreover, for relaxing (but not stimulating) acupressure, these changes were associated with improvements in sleep quality.

## Risk Assessment

The known or expected risks are risk of bruising at points of pressure; there is a very small chance (<1%) of having bruises at points of pressure if too much pressure is applied. This bruising should not continue or get worse. The researchers will try to minimize the risk of bruising by having the acupressure app demonstrate the correct amount of pressure to apply at the start of the study. Additionally, a member of the research team will call the participant at certain times during the study to evaluate their health and safety. During these conversations the study coordinator will ask the participant about any bruising.

**Risk lowering measures:** Study procedures to manage or minimize risks include a vibration feature installed in the

AcuWand programming to signify or “warn” participants that minimum pressure has been achieved.

The AcuWand is not FDA approved, nor are we seeking FDA approval for its use. We do not anticipate any problems with the device which would cause injury or harm in any way.

## Benefit Assessment

Participants may not receive any personal benefits from being in this study. However, it is possible that the acupressure treatments could reduce the severity of fatigue they are experiencing. We hope the information learned from this study will benefit other ovarian cancer patients.

## HYPOTHESES AND OBJECTIVES

We are proposing to evaluate the impact of **six weeks of daily self-administered relaxing acupressure** on fatigue, sleep, and quality of life in persistently fatigued ovarian cancer survivors compared to 6 weeks of daily self-administered sham acupressure or no treatment. Survivors who have fatigue starting at or after cancer diagnosis, and have ≥4 on the Brief Fatigue Inventory, which is the cutoff for moderate fatigue, will be eligible for the study. During the study period we will randomize and follow 171 survivors (we anticipate a ~13 % dropout with the goal of 150 completers). We hypothesize that persistently fatigued ovarian cancer survivors will experience improvements in fatigue, sleep, quality of life, and symptoms commonly associated with persistent fatigue from utilizing relaxing as compared to sham acupressure or no treatment.

## 2.0 SPECIFIC AIMS

To investigate our hypothesis, we will randomize fatigued ovarian cancer survivors into 6 weeks of daily: 1. Relaxing self-acupressure (n=57); 2. Sham self-acupressure (n=57); or 3. No treatment (n=57) followed by 18 weeks of no acupressure and investigate the following aims:

1. Examine the effect of 6 weeks of daily self-administered relaxing acupressure compared to self-administered sham acupressure or no treatment on:

- A. Persistent fatigue (**Primary aim**) -- measured with The Brief Fatigue Inventory;
- B. Quality of life (**Secondary aim**) -- using the Functional Assessment of Chronic Illness Therapy Measurement System, specifically the ovarian cancer specific instrument;
- C. Sleep Quality (**Secondary aim**) -- using the Pittsburgh Sleep Quality Index;
- D. Symptoms commonly associated with persistent fatigue (**Exploratory aim**) (sleep disturbance, pain, cognitive function, mood, and female sexual function) -- using Patient Reported Outcomes Measurement Information System.

**2 (Exploratory aim).** To investigate the duration of effect self-administered relaxing acupressure as compared to self-administered sham acupressure or no treatment during the 18 weeks following the end of acupressure treatment (carry-over phase) on persistent fatigue, quality of life, sleep quality, and symptoms commonly associated with persistent fatigue (sleep disturbance, pain, cognitive function, mood, and female sexual function) using the measurement tools described for the primary aim.

Both acupressure treatments will be delivered via the MeTime Acupressure app in association with the AcuWand.

## 3.0 METHODS

**Study Design.** We propose a randomized, controlled clinical trial comparing relaxing acupressure to sham acupressure and no treatment for persistent fatigue in ovarian cancer survivors. The study will be 25 weeks in

duration: **Phase I (screening phase;** 7 days in duration/weeks -1 to 0), consisting of telephone screen for study eligibility, obtaining informed consent, random assignment to treatment group, and shipment of computer tablet and AcuWand, if appropriate; **Phase II (active treatment phase;** 6 weeks in duration), which will consist of performing once daily self-acupressure—sham or relaxing—with the study app and the AcuWand or no treatment with outcomes including baseline and 6-week subjective measures of fatigue; sleep quality, pain, female sexual function, cognition, and quality of life; **Phase III (carry-over phase)** is an 18-week follow-up to evaluate fatigue, sleep quality, pain, female sexual function, cognition, and quality of life after completion of the acupressure treatments with outcomes assessed at 12 and 24 weeks. Our studies have indicated that the effects of self-acupressure can persist for 4 weeks after the end of treatment and acupuncture interventions in chronic pain populations have seen sustained effects ranging from 6 months to one-year post-intervention. As such, we intend to determine if acupressure has sustained impacts beyond 4 weeks after the end of treatment. **All groups including the no treatment group will have an equal number of study contacts.**

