### **3.2 Randomization.**

The biostatistician will provide sealed envelopes for the randomization of all participants. Participants will be

randomized to one of the three study arms: Acupressure, Sham acupressure or Control. A random generator for block stratified randomization in blocks of 6 participants will be programmed by [name], the study statistician. Eligible patients will be randomized into one of three groups - relaxing acupressure, sham acupressure, or no treatment - in a 1:1:1 ratio for a total of 171 participants with 57 randomized into each group.

We will be delivering our self-acupressure interventions (relaxing and sham) using our modified MeTime Acupressure mobile app. We will rename the MeTime Acupressure app to "Study App" and change the icon so participants will not be able to locate it in the Apple or Google Play Stores and unblind themselves. In association with the 3D Media Lab at the University of Michigan we will create a mobile app for our sham acupressure points. The sham and relaxing acupressure apps will be identical in all aspects except for the acupoint locations. For women randomized into the "no treatment arm" they will receive the acupressure app and AcuWand at the end of their study participation. The acupressure app will be loaded onto computer tablets by our computer information technology (IT) support person. Women in the acupressure arms will also receive an AcuWand to be used in association with the acupressure app to help women apply the correct amount of pressure to acupoints. The women will receive directions within the acupressure app on how to use the AcuWand. The AcuWand has been designed to use two lithium-ion long lasting (up to one year with normal use) batteries. Participants are asked to return the AcuWand with provided materials at no cost to them in order to upload data about frequency, duration and amount of pressure of acupressure applications. Of note: no Wi-Fi connection is needed to use the acupressure app and our IT support person will be available to help participants who are unfamiliar with or have any issues with their tablet, AcuWand or the app.

**Relaxing Acupressure.** There are 5 acupoints with 4 of the acupoints performed on both the left and right sides of the body (total of 9 points to stimulate; see Figure 7). Each of the 9 acupoints will be stimulated for 3 minutes per point

with the AcuWand giving a total treatment time of 27 minutes daily. The relaxation acupoints are:

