### 3.3 Blinding.

Our IT support person will place the computer tablets—already loaded with either the acupressure app--sham or relaxing--or the “no treatment” message and the AcuWands into opaque shipping boxes per our randomization code, i.e., a tablet with the sham acupressure app loaded on it would be placed in a shipping box labeled with a study ID assigned to the sham arm. The outside of the shipping boxes will be labeled with study IDs. This will ensure that only our IT support person will be unblinded, but all study staff and researchers will remain blinded until after the completion of data analyses. The IT support person will not be responsible for collecting or analyzing any study data. Participants in the “no treatment” arm will not be blinded; however, the two self-acupressure arms will be blinded as to which acupressure treatment they have been randomized. The MeTime app will be re-named to “Study App” for the study.

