**Table 2**

	Screening phone call	Baseline Week 0	Treatment Phase Weeks 1 - 6	Follow-up Week 6 (- 2 days/+5 days)	Follow-up Week 12 (- 2 days/+5 days)	Follow-up Week 24 (- 2 days/+5 days)
Phone Screen	X					
Screening Survey	X					
BFI	X	X		X	X	X
PHQ-2	X					
Consent	X					
Pt. Info & Dem.	X					
Concomitant of Medications		X				
Diagnosis & Treatment of initial cancer		X				
FACT-O		X		X	X	X
PSQI		X		X	X	X
PROMIS		X		X	X	X
IPAQ		X				
SCQ		X				
FSQ		X				
MAIA		X		X		
Daily Logbook			X			
Acupressure Fidelity				X		
Assessment of blinding				X		
AcuWand Comfort				X		
Final Evaluation						X

**Administering Study Assessments.** All potential participants will be screened over the phone using a brief questionnaire to confirm eligibility for the study. Enrolled participants will then receive an email link to their RedCAP study measures at baseline, weeks 0, 6, 12 and 24. All the surveys will be administered at all-time points with the exception of descriptive and baseline assessments, which will only be collected at week 0; fidelity, blinding and adherence, which will only be asked at week 6; and a final evaluative questionnaire about the participants' perception of the study and the use of the AcuWand device. Adverse events will be collected at all-time points. Inspirational reminder emails, texts, or phone calls (as appropriate for a given participant) will be made to encourage the highest possible response rate to each round of study assessments. Participants without an email account will be assisted in obtaining a free Gmail account and how to access it on their computer tablet by study staff. Those participants who do not have access to Wi-Fi will be assisted in finding free Wi-Fi in their community (e.g., public library, Starbucks, McDonalds, etc.) IT study staff will be available to assist participants with any questions that may arise. E-mail is required so that study instruments may be accessed through surveys in RedCAP.

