### 7.2.4. Lost to follow-up after enrollment but withdrew before the baseline visit

Participants who withdraw between enrollment and the baseline visit can be replaced with a new participant

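### Nothing requires the week-0 survey to be submitted before allocation or before the arm-revealing box is opened, so baseline BFI may be rated with the arm known

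*Combined protocol and SAP*

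**What the plan says.** **Order of steps.** Section 3.0 (Study Design) defines Phase I as "7 days in duration/weeks -1 to 0" and includes in it "obtaining informed consent, random assignment to treatment group, and shipment of computer tablet and AcuWand, if appropriate". Phase II, the active treatment phase, is described "with outcomes including baseline and 6-week subjective measures of fatigue". Table 2 agrees: BFI and consent belong to the screening call, and BFI is taken again at week 0. Under Administering Study Assessments (Section 4.1), "Enrolled participants will then receive an email link to their RedCAP study measures at baseline, weeks 0, 6, 12 and 24".

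**What the box shows.** Section 3.3 has the IT support person place the tablet loaded with an app or the no-treatment "message and the AcuWands into opaque shipping boxes per our randomization code". Of women in the no-treatment arm, Section 3.2 says "they will receive the acupressure app and AcuWand at the end of their study participation". Section 3.3 states that this arm is not blinded and that the two acupressure arms are blinded only to the type of acupressure.

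**Use of week 0.** Section 4.1 gives the BFI a 24-hour recall. The Statistics Section makes week 0 one of four levels of the outcome and tests group by week. Section 9.1 makes baseline BFI a condition of being evaluable. The screening BFI is taken before consent, for eligibility, and has no role in the model.

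**What is absent.** No section requires the week-0 survey to be submitted before allocation, shipment or opening of the box.

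**The concern.** A baseline in a partly open-label trial should be recorded before the participant can know her arm. Here the listed order allows the reverse. A woman who opens a box holding a no-treatment message and no AcuWand may rate her fatigue over the last 24 hours differently from one who finds an app and a device. Because week 0 is part of the outcome vector, a difference arising that way is read by the group-by-week test as a difference in change.

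At stake are the comparisons of relaxing and of sham acupressure with no treatment. Relaxing versus no treatment is part of the primary aim. The box does not distinguish relaxing from sham, so that contrast is largely protected while blinding holds. FACT-O, PSQI and PROMIS are collected at the same week-0 survey. PSQI (past month) and most PROMIS forms (seven days) are probably less sensitive than BFI because of their longer recall.

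**Working it through.** **1. The plan's own figures.** The planned difference between relaxing and no treatment at end of treatment is 4.5 - 2 = 2.5 points (Section 9.0). Table 3 gives 1.9621 - 0.4336 = 1.5285, which matches Table 4. The stated interaction power above 95% with 50 per arm also reproduces: 98.3% using weeks 0 and 6 with subject and residual variances of 4 each. None of these figures is in dispute; they set the scale.

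**2. How a shift enters.** Let s0 and s6 be the mean shifts in reported BFI due to knowing the arm, for no treatment (N) and acupressure (A). The bias in the week-6 change contrast, A minus N, is

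bias = (s0N - s6N) - (s0A - s6A).

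The week-0 shift therefore passes through in full only if it is differential and absent at week 6. If knowing the arm moves both ratings equally, it cancels. If a share p of the arm rates after opening the box and each such woman shifts by d, then s0N = p × d. A positive value (no-treatment women report more fatigue at week 0) works against acupressure; a negative value favours it.

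**3. Size, by assumption.** The documents give neither p nor d. With every woman exposed and d of 0.3 to 0.5, the bias is 0.3/2.5 = 12% to 0.5/2.5 = 20% of the planned difference, or 0.3/1.53 = 20% to 0.5/1.53 = 33% of the Table 4 difference. With p = 20%, it is 0.06 to 0.10 points, or 2.4 to 4% of 2.5.

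**4. False-positive rate of one comparison with no treatment.** Inputs: 50 per arm; SD of change 1.7 (Section 9.2) or √(2 × 4) = 2.83 (Section 9.0, reading the residual variance as 4). SE = SD × √(2/50), which is 0.34 or 0.566. Rate = Φ(-z + b/SE) + Φ(-z - b/SE), where b is the net bias from step 2 and z is 1.96 or 2.576.

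| b (points) | 5% level, SD 1.7 | 5% level, SD 2.83 | 1% level, SD 1.7 | 1% level, SD 2.83 |
|---|---|---|---|---|
| 0.25 | 11.4% | 7.3% | 3.3% | 1.8% |
| 0.5 | 31.3% | 14.3% | 13.5% | 4.6% |
| 1.0 | 83.7% | 42.4% | 64.3% | 20.9% |

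At b = 0.10, b/SE is 0.294 or 0.177, and the rate at the 5% level is 6.0% or 5.4%.

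**5. Which analysis removes it.** A simulation (4,000 runs per setting, two arms of 50, no true effect, intra-class correlation 0.5, shift at week 0 only) gave these results for a 0.5-point shift:

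- Change from week 0: bias 0.51.
- ANCOVA on the shifted week-0 score: bias 0.26, so about half remains.
- ANCOVA on a BFI taken before allocation: bias below 0.01.

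For that last analysis the false-positive rate was 4.7 to 5.1% at the 5% level and 0.8 to 1.0% at the 1% level, across shifts of 0.5 and 1.0. The simulation did not impose the eligibility cut-off of 4 on the screening score; regression to the mean from that cut-off should fall on all arms alike.

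**The case against.** The strongest reply is that the order is inferred. Section 3.0 lists activities by phase, Phase I ends at the same week 0 where Table 2 puts baseline, and shipment is not receipt. The survey link goes out by email and needs no box. All of this stands, so the point is about what the plan permits.

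Three stronger readings do not hold.

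- **That some women must open the box to reach the survey.** The plan says "Participants without an email account will be assisted in obtaining a free Gmail account and how to access it on their computer tablet", which might suggest this. But Section 8.0 lets surveys be opened on an electronic device, keeps them separate from the acupressure app, and provides for phone administration. The tablet is not shown to be needed for baseline.
- **That Section 7.2.4 shows allocation is known before baseline.** It says "Participants who withdraw between enrollment and the baseline visit can be replaced with a new participant". This separates enrolment from baseline; it does not say when the allocation is drawn or revealed.
- **That the shift enters one for one.** The no-treatment arm rates week 6 with the same knowledge, and acupressure women also learn they have acupressure. Only the net term in step 2 of the working counts.

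It is also fair to say that a large assumed shift need not overturn the comparison of most interest. Moving 1.53 toward zero by 0.5 gives 1.03 with SE 0.362, a 95% interval of about 0.31 to 1.75 and p of about 0.005. Sham versus usual care in Table 4 would fall to 0.865 - 0.5 = 0.365 with SE 0.353 and lose significance, though Aim 1 does not name that contrast.

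What remains is that no rule prevents the exposure, and such a rule costs little.

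**Conclusion.** The plan leaves open that the week-0 BFI is rated after a woman knows whether she has acupressure or no treatment. Any resulting shift that differs between arms and is not also present at week 6 biases the contrasts with no treatment. A reader might infer that such bias has occurred, or that it amounts to 12 to 33% of the effect. The documents support neither: they do not say when boxes are opened relative to the survey, and they give no shift size. The 0.3 to 0.5 points is an assumption about a whole-arm mean, its direction is unknown, and it shrinks in proportion to the share of women exposed. The false-positive rates in the working rest further on 50 per arm, an SD of change between 1.7 and 2.83, and no matching shift at week 6. The point merits a change because the protection is simple and specific.

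**What to change.** **Before allocation.** State in Sections 3.0 and 3.2 that the week-0 survey must be submitted, on the participant's own device or by phone as Section 8.0 allows, before the allocation is drawn and the box shipped. This protects all week-0 measures. It reorders steps around the end of the 7-day screening phase and costs a slight delay to shipment.

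**For women already enrolled.** Add a BFI sensitivity analysis in which the pre-consent screening BFI replaces week 0 as the baseline covariate and week 0 is removed from the outcome vector, leaving weeks 6, 12 and 24. Adding the screening score while week 0 stays among the outcomes would leave the bias in place. The score is already collected, so the cost is one extra model. Report the date of each week-0 survey against the date of box delivery where both were recorded, so that the share possibly exposed can be seen. If enrolment is complete, only these steps remain.

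**Limits.** The sensitivity analysis removes week-0 contamination for BFI only. It does not remove open-label reporting bias at week 6; where knowing the arm shifts both ratings alike, it would expose the week-6 shift that the change contrast cancels. It cannot be done for FACT-O, PSQI or PROMIS, which have no screening measurement in Table 2.
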